1.3 Research hypothesis

Based on preliminary data showing that the presence of HPV antigens is contributing to increased anti-tumor T cell activity in patients with SCCHN, we hypothesize that immunotherapy with PD-L1 antibody will lead to more intense and efficient specific immune activation against the SCCHN tumor in HPV + patients compared with HPV - patients. We also hypothesize that an extensive analysis of the blood and saliva might lead to identification of markers predictive of a more efficient response to PD-L1 inhibition. Lastly we would like to test the ability of PET scan to detect an increased immune response. One can hypothesize that a corresponding increase in the immune response with an increase in the number of infiltrative activated immune cells could be associated with an increase in metabolic activity measured by PET SUV. Similarly, an effective anti-tumor activity of the

activated immune response could lead to decreased metabolic activity. We are interested in evaluating the dynamic in the metabolic activity early in the treatment and to attempt to detect potential consistency that could be used in future therapeutic paradigms.

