2. STUDY OBJECTIVES

2.1 **Primary objectives**

- 2.1.1 The primary objective of this study is to investigate the effect of Durvalumab on local and systemic immune activation by HPV status in patients with oral cavity and oropharynx HNSCC. This will be done by:
 - a) Examining the effects of Durvalumab on systemic immune response to HPV and tumor associated antigens
 - b) Examining the effects of Durvalumab on immune regulatory mechanisms.
 - c) Exploring the association between levels of immune-regulatory miR in plasma and saliva and immune response.

Results will be compared between HPV positive and negative patients to identify a possible differential effect of treatment with Durvalumab. Level of local immune response in the primary tumor and in the regional lymph nodes will be compared whenever possible.

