Tumor (primary tumor and involved lymph node) will be assayed using standing immunofluorescence techniques for PD-1+CD4+, PD 1+CD8+, PD-1L+, and Foxp3+CD4+ tumor-infiltrating cells. The results will be quantified (0 to 3+).

Immunohistochemical staining will be carried out on 4µm-thick sections utilizing an Autostainer Plus (Dako - Agilent Technologies) with appropriate positive and negative controls. Sections are baked for 60 minutes at 60 °C in a dehydration oven and heat-induced epitope retrieved in the PT link (Dako – Agilent technologies) using EnVision FLEX target retrieval solution for 20 minutes at 97 °C then cooled to room temperature in TBST Wash buffer for 5 minutes. Slides are incubated with the diluted antibodies. Antibody detection will utilize the Envision FLEX kit (K8023) with a DAB chromagen for visualization according to the manufacturer's instructions (Dako – Agilent technologies). Slides are then counterstained with hematoxylin. The percentage of tumor which have an infiltrate of lymphocytes or macrophages will be estimated and the average number of positive immune cells per high power field (HPF) in a minimum of 4 representative HPF areas will be determined utilizing a semi-quantitative four tiered scale used for scoring lymphocytes (0= no lymphocytes, 1= 1-10/HPF, 2= 11-50/HPF and 3= >50/HPF) and macrophages (0= no macrophages, 1= 1-50/HPF, 2= 50-100/HPF and 3=>100/HPF). Lymphocyte and macrophage infiltrate scores are obtained by multiplying these scores to attain a score from 0-300.

miRNA will be quantified in tumor tissue and involved lymph node using PCR-based techniques (as described in 8.3.1).

Remaining tissue samples will be retained for future research after the study report has been finalized if agreed by patients in the ICF. Otherwise it will be disposed.

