9.2 Immunologic response

1. Effect of Durvalumab on systemic immune response to HPV and tumor associated antigens

Blood will be collected before and after treatment (before surgery) with Durvalumab. Peripheral blood mononuclear cell interferon- γ production in vitro (ELISA) in response to commercially available peptide pools corresponding to HPV, p53, Mage-A3, Her2/neu, and survivin will be measured by commercially available ELISA kits. Responses of patients whose tumor are HPV+ will be compared to those that are HPV-.

2. Examine the effects of Durvalumab on immune regulatory mechanisms:

- Blood samples will be collected before and after treatment with Durvalumab. The following immune effector and regulatory responses will be assessed in blood using standard flow cytometric techniques:

CD4+, CD8+, CD4+FoxP3+ Treg, and CD45RO+CD4+ memory T cells; CD3-CD56+ NK cells, and CD14-HLA-DR-CD15+ MDSC. Average change in pre- and post-treatment measurements will be compared between HPV+ and HPV- patients.

- Tumor (primary tumor and regional involved lymph nodes) will be collected before treatment (tissue biopsy) and at the time of surgery, after treatment. PD-1+CD4+, PD 1+CD8+, PD-1L+, and Foxp3+CD4+ tumor-infiltrating cells will be quantified (0 to 3+) using standing immunofluorescence techniques. The results of patients whose tumor are HPV+ will be compared to those that are HPV-.

3. Explore the association between levels of immune-regulatory miR in plasma and saliva and immune response. Blood and saliva samples will be collected before and after treatment with Durvalumab. Tumor (primary tumor and regional involved lymph nodes) will be collected before treatment (mandatory biopsy) and at the time of surgery. Levels of immune-regulatory miRs will be quantified using PCR-based techniques. Levels and change in levels before and after treatment will be compared among saliva, blood and tumor tissue.

The relationship between levels of the miRs and the immune response to HPV, immune response to tumor associated antigens, and immune regulatory molecules/cells will be assessed.

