 - b. Tumor (primary tumor and regional involved lymph nodes) will be collected before treatment and at the time of surgery, after treatment. PD-1+CD4+, PD 1+CD8+, PD-1L+, and Foxp3+CD4+ tumor-infiltrating cells will be quantified (0 to 3+) using standing immunofluorescence techniques.
- 3. Immune-regulatory miR response.
 - a. Levels of immune-regulatory miRs in blood, saliva and tumor (primary and regional involved lymph nodes) will be quantified using PCR-based techniques.

Secondary Endpoints

There are two types of secondary endpoints.

The first consist of measures of tumor volume (via CT scan) or metabolic activity (via PET scan).

The second are measures of clinical toxicities that may occur during the trial.

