11.2.2 Efficacy Analyses

As stated above, there are several primary efficacy measures for this protocol. In addition, this is not a randomized clinical trial, thus there is not one primary efficacy analysis, rather there are a series of primary analyses proposed to be performed examining each of the primary efficacy measures described above.

Analysis of immunogenicity

- Peripheral blood mononuclear cell interferon-γ production in vitro (ELISA) in response to commercially available peptide pools corresponding to HPV, p53, Mage-A3, Her2/neu, and survivin will be compared between patients who are HPV+ and HPV- using 2 sample t-tests. These measures will be compared in several ways. First, baseline, pre-treatment levels will be examined using descriptive statistics (n, mean, standard deviations, range). These measures will be examined overall and by HPV (+/-) groups. For each measure, and time point, 95% confidence intervals will be estimated. Next, two sample t-tests will be performed to compare levels of the measures at baseline. Next, measures taken post-treatment will be examined in a similar manner (descriptive statistics and 2-sample t-tests). Finally, comparisons between HPV+ and HPV- groups will be made by comparing the changes (pre-treatment to posttreatment) between groups using 2-sample t-tests.
- 2) Concentration of certain immune effector and regulatory cells will be assessed in blood (CD4+, CD8+, CD4+FoxP3+ Treg, and CD45RO+CD4+ memory T cells; CD3-CD56+ NK cells, and CD14-HLA-DR-CD15+ MDSC) pre- and post- treatment. Descriptive statistics, confidence intervals will be calculated and 2-sample t-tests will be performed as described above for the interferon- γ analyses.
- 3) Tumor-infiltrating immune-regulator and effector cells will be quantified (0 to 3+) using standing immunofluorescence techniques. Counts and percents will be calculated for these measures overall and by HPV (+/-) groups pre- and post-treatment. Fisher exact tests will be used to compare groups at pre- and post- treatment. Stuart-Maxwell tests (generalizations of the McNemar's Test) will be used to examine changes between groups (HPV +/-) from pre- to post- treatment.

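### The Stuart-Maxwell test cannot compare change between HPV groups, so the tumor-infiltrating cell scores have no valid test of a differential effect

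*Combined protocol and SAP*

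**What the plan says.** The primary objective in section 2.1, repeated in section 11.1, includes a comparison by HPV status: "Results will be compared between HPV positive and negative patients to identify a possible differential effect of treatment with Durvalumab". The research hypothesis in section 1.3 is also comparative: treatment "will lead to more intense and efficient specific immune activation against the SCCHN tumor in HPV + patients compared with HPV - patients".

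Endpoint 2b is an ordered four-level score, because "tumor-infiltrating cells will be quantified (0 to 3+) using standing immunofluorescence techniques". It is measured in each patient's biopsy before treatment and surgical tissue after treatment. Section 11.2.2 item 3 plans three things for it:

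- counts and percentages overall and by HPV group, before and after treatment;
- Fisher exact tests between the groups at each of the two time points;
- for change: "Stuart-Maxwell tests (generalizations of the McNemar's Test) will be used to examine changes between groups (HPV +/-) from pre- to post- treatment".

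For the interferon-gamma measures, item 1 ends differently: "comparisons between HPV+ and HPV- groups will be made by comparing the changes (pre-treatment to posttreatment) between groups using 2-sample t-tests". Items 2 (blood cells) and 4 (miRs) adopt the item 1 methods by reference. Item 3 does not.

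**The concern.** The sentence on Stuart-Maxwell gives a one-sample paired test a two-sample job. HPV+ and HPV- patients are different people, so they cannot form the rows and columns of a paired table. Only the pre- and post-treatment scores of the same patients can.

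An analyst following the sentence has two options, and neither compares change between groups. Testing each HPV group separately invites reading one significant and one non-significant result as an HPV difference. It can also hide opposite effects, because the test has no direction. Pooling the patients detects any common change and discards HPV status altogether.

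What is at stake is the answer to the differential-effect question for the only primary endpoint that scores immune cells in the tumor itself.

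**Working it through.** **Plan's own figures.** The plan gives no power or precision figure for endpoint 2b. The 80% power at 1.3 SD in section 11.3 is for a 2-sample t-test: the noncentral t distribution (18 df, noncentrality 1.3/√(2/10), two-sided 0.05) gives 78.5%, close to the stated value. It does not cover a 0 to 3+ score.

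**Inputs.** 10 HPV+ and 10 HPV- patients (section 11.3); scores 0 to 3 (section 11.1); paired pre and post tissue (section 11.1.2). All patterns of change below are constructed examples or assumptions; the documents give none.

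**What the test uses.** Stuart-Maxwell forms the differences d between the row and column totals of one pre-by-post table and refers d′S⁻d to chi-square. Every entry is a count of patients by pre and post score, and HPV status appears nowhere. In a pooled data set with opposite change in the two groups, 500 random reassignments of the HPV label left the statistic unchanged.

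**Within-group reading, two categories.** With k patients rising one step and none falling, the exact p is 2 × (1/2)^k. The direct comparison is an exact Wilcoxon-Mann-Whitney (WMW) test on each patient's change.

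| Change, group 1 vs group 2 | Within-group p | Direct comparison p |
|---|---|---|
| 6/10 up vs 3/10 up | 2/64 = 0.031 vs 2/8 = 0.25 | 0.37 |
| 8/10 up vs 8/10 down | 2/256 = 0.008 in both (chi-square 8 on 1 df: 0.005) | 0.00006 |

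The first row suggests a difference that the direct comparison does not support. The second row shows identical p-values for opposite effects.

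**Within-group reading, four categories.** With baseline scores 0,0,0,1,1,1,2,2,1,0 and the first k patients rising one step, exact Stuart-Maxwell gives p = 0.0625 for k = 7 and 0.031 for k = 8. So 8/10 against 7/10 rising puts one group below 0.05 and the other above it, while the direct comparison gives p = 1.0.

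**How often exactly one group is significant when there is no difference.** Let both groups have the same chance π of a one-step rise, with no falls (assumption). In the two-category exact test a group is significant when at least 6 of 10 rise, so s = P(X ≥ 6) with X ~ Binomial(10, π). The chance that exactly one group is significant is 2s(1 − s).

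| π | s | 2s(1 − s) |
|---|---|---|
| 0.3 | 0.047 | 9% |
| 0.4 | 0.166 | 28% |
| 0.5 | 0.377 | 47% |
| 0.6 | 0.633 | 46% |
| 0.7 | 0.850 | 26% |
| 0.8 | 0.967 | 6% |

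Exact WMW on change rejects in about 1% of the same trials.

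A simulation with the chi-square Stuart-Maxwell test gives a similar picture (four categories, baseline uniform on 0 to 2, 3,000 trials per setting). At a common rise chance of 0.6, 0.7 and 0.8, exactly one group was significant in 39%, 51% and 40% of trials. A rank test on change rejected in 3% to 4%.

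**Pooled reading.** If 8/10 rise in both groups, 16 of 20 patients rise; the two-category chi-square is 16 on 1 df, p = 0.00006, although change is identical. With opposite change, rises and falls cancel: p = 1.0, where the direct comparison gives 0.00006.

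**Fisher at post-treatment.** If 8/10 against 2/10 patients sit at score 2 at both time points and nobody changes, p = 0.023. That is a valid difference in level and says nothing about treatment effect.

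**The case against.** The strongest reply is that the authors meant a within-group pre/post test, worded loosely, in a pilot whose stated goal is descriptive. Section 11.1 disclaims a single primary efficacy analysis, no sample size or stopping rule rests on endpoint 2b, and counts by group are planned. The plan never says that one significant and one non-significant result will be read as an HPV difference, so the percentages above are rates for a possible misreading, not error rates of a planned procedure. This stands, and it limits the severity. It does not remove the defect: section 11.2.2 calls these primary analyses, the sentence says between groups, and the within-group reading leaves the comparison of change unaddressed.

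The illustrations also depend on choices the plan does not make. In the four-category example, 6/10 rising gives an exact p of 0.0625, so the 6-against-3 contrast holds only in two categories. With the uncorrected chi-square McNemar test, significant from 4 risers, the exactly-one-significant rates for π from 0.3 to 0.8 become about 46%, 47%, 28%, 10%, 2% and 0.2%. The peak is the same, but it falls at smaller π. The 1% for exact WMW partly reflects its conservatism with heavy ties. These points change the profile, not the conclusion.

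Section 9.2 might seem to show that tumor cells were deliberately treated differently, since for blood cells it says "Average change in pre- and post-treatment measurements will be compared between HPV+ and HPV- patients" and for tumor cells it speaks only of results. But it describes the interferon-gamma comparison without mentioning change either, although item 1 does test change. The case therefore rests on section 11.2.2 alone.

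**Conclusion.** The concern holds. Item 3 does name a test for change between HPV groups, but that test cannot address the question, and nothing elsewhere in the documents supplies one. Items 1, 2 and 4 each have a between-group test of change; endpoint 2b does not.

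The consequence is a missing or misleading answer on whether tumor infiltration changes differently by HPV status. Under equal change in both groups, a contrast of within-group significance could mislead in up to about half of trials, on assumed rise probabilities and depending on the version of the test. The defect itself needs no assumption, because it follows from what Stuart-Maxwell tests. It should be fixed, with consequences confined to this endpoint family in a descriptive pilot.

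**What to change.** Reword section 11.2.2 item 3 as follows.

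1. For each cell phenotype, compare HPV+ with HPV- on each patient's pre-to-post change in score, using an exact Wilcoxon-Mann-Whitney or permutation test. Report the difference in the proportion of patients whose score rises (or a probability index) with a 95% confidence interval. A Hodges-Lehmann shift is unreliable on heavily tied 0 to 3 data and is best avoided.
2. State that Stuart-Maxwell, in an exact version, or a signed-rank test is used within each HPV group only.
3. Show the pre-by-post table for each HPV group, since a patient starting at 3+ cannot rise.

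This is workable at 10 per group, though only large differences will show. 8/10 against 2/10 rising gives p = 0.023 and a difference of 60 points (Newcombe 95% CI 16 to 80). 6/10 against 3/10 gives p = 0.37 and 30 points (−12 to 60).

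There are two drawbacks. A rank test on change treats every score step as equal, and the steps are unequal if the score is the lymphocyte scale in section 8.3.4 ("0= no lymphocytes, 1= 1-10/HPF, 2= 11-50/HPF and 3= >50/HPF"). The proportion rising ignores the size of a rise. The tables in step 3 let the reader see both.

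The cost is a few more lines of SAP text, with no new samples, assays or patients.

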11.3 Determination of sample size

The goal for this pilot study is to get preliminary descriptive data for a series of measures taken using blood, saliva and tumor tissue pre- and post- immunotherapy. With a sample size of 10 patients in each group (i.e. 10 with HPV+ and 10 HPV-) a 95% confidence interval for each group will have confidence limits $\pm - 0.72$ standard deviations. In addition, the change in each measure (pre- versus post- therapy) can be used to estimate 95% confidence intervals to determine whether there are any significant changes from baseline (i.e., the measure increased (or decreased) by more than 0.72 standard deviations).

Furthermore, to compare groups (HPV+ versus HPV-), there is 80% power to detect a difference in measures equal to 1.3 standard deviations of the measure of interest using a 2-sample t-test with alpha=0.05.

The patients who are discontinued from the study treatment and/or from the study will be replaced.

It is anticipated that an accrual rate of 12 patients per year is reasonable and thus the goal of 20 evaluable patients should be achieved within approximately 18 months. Additional 6 mo might be needed for accruing replacement patients for the patients unable to complete study treatment or required investigations.

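### The Stuart-Maxwell test named for change in the 0 to 3+ tumor-infiltrate score cannot compare the HPV groups, and within a group of 10 it ignores the order of the levels and has low power.

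*Combined protocol and SAP*

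**What the plan says.** Section 11.1 lists endpoint 2b among the primary endpoints: several "tumor-infiltrating cells will be quantified (0 to 3+) using standing immunofluorescence techniques", before treatment and at surgery.

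Section 11.2.2 item 3 gives the analysis in three parts:

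- Description: "Counts and percents will be calculated for these measures overall and by HPV (+/-) groups pre- and post-treatment".
- Fisher exact tests between the HPV groups at each time point.
- Change: "Stuart-Maxwell tests (generalizations of the McNemar's Test) will be used to examine changes", which the sentence goes on to describe as changes between the HPV+ and HPV- groups from before to after treatment.

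It gives no exact version of the change test, no use of the ordering of the score, and no rule for levels that nobody occupies.

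Section 11.3 sets 10 patients per HPV group, with discontinued patients replaced. It says that confidence intervals for the change in each measure can be used "to determine whether there are any significant changes from baseline (i.e., the measure increased (or decreased) by more than 0.72 standard deviations"). For the group comparison it claims "80% power to detect a difference in measures equal to 1.3 standard deviations of the measure of interest using a 2-sample t-test with alpha=0.05". It states no level or power for the Stuart-Maxwell test.

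**The concern.** Two things are wrong with the named test.

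First, Stuart-Maxwell takes a single pre-by-post table and asks whether its two margins agree. HPV status does not enter the statistic, and HPV+ and HPV- patients are not matched pairs. The plan words the test as a comparison of changes between the groups, which it cannot make. The Fisher tests compare groups only at each time point. So the HPV contrast of change in this endpoint, which belongs to the primary objective, has no usable test.

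Second, within one HPV group the test is a large-sample chi-square with up to 3 degrees of freedom, it treats four ordered levels as unordered, and it would be applied to 10 patients. A consistent rise in infiltrating cells could easily be reported as no significant change. Since the synopsis wants the pilot to indicate which measures the drug affects most, tissue markers could be passed over for this reason alone.

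**Working it through.** **Inputs.** From the documents: four ordered levels (11.1, 11.2.2), 10 patients per group (11.3), Stuart-Maxwell for change (11.2.2). Assumed, because the documents are silent: two-sided 5%, the distribution of patients over levels, and the pre-post correlation.

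**1. The plan's own figures.** Half-width of a 95% interval for a mean: t(0.975, 9)/√10 = 2.262/3.162 = 0.715 SD, stated as 0.72. Power of the two-sample t-test at 1.3 SD: noncentrality 1.3 × √(10/2) = 2.907 on 18 df gives 78.5%, close to the stated 80%. Both figures concern means and t methods. Neither describes the test chosen for the 0 to 3+ score.

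**2. Upper bound on the statistic.** Q = d′S⁻d, where d is the vector of differences between post and pre margins, s_ii = n_i. + n_.i − 2n_ii and s_ij = −(n_ij + n_ji). Give each patient a vector x (+1 at the post level, −1 at the pre level, zero if unchanged). Then d = Σx and S = Σxx′, so Q is the squared length of a projection of a vector of ones, one for each patient who changed. Hence Q ≤ m, the number of patients who change level. No distribution is assumed.

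| Levels in play | df | 5% critical value | Fewest changers needed |
|---|---|---|---|
| 4 | 3 | 7.81 | 8 of 10 |
| 3 | 2 | 5.99 | 6 of 10 |
| 2 | 1 | 3.84 | 4 of 10 |

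**3. Worked tables.** All changers rise one level, none fall, and the moves are spread over the three boundaries. Here Q = m, and the exact signed-rank p is 2/2^m.

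| Rise | Stuart-Maxwell p (3 df) | Exact signed-rank p |
|---|---|---|
| 6 of 10 | 0.112 | 0.031 |
| 7 of 10 | 0.072 | 0.016 |
| 8 of 10 | 0.046 | 0.008 |

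The last two rows also show why separate group tests are no substitute for a group comparison. With 8 risers in one HPV group and 7 in the other, one result is significant and the other is not, although the groups differ by one patient.

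**4. Empty levels.** If 4 of 10 move from 1 to 2 and the rest stay, Q = 4 and S is singular. With df equal to the rank of S, p = 0.046; with 3 df, p = 0.26; the exact p is 2/2⁴ = 0.125. In simulated null tables of 10 patients, S was singular in 4-77%, depending on the assumed distribution and correlation. One standard routine returned no p-value for such a table.

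**5. Power.** Latent bivariate-normal scores were cut into four levels under four assumed distributions (uniform, low-heavy, mid-heavy, skewed), with n = 10 and rank-based df. Shifts are in SDs of the latent score at one time point; at correlation 0.5 the change has the same SD, since 2(1 − 0.5) = 1.

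| Correlation | Shift (SD) | Stuart-Maxwell | Exact signed-rank | Share of signed-rank findings missed |
|---|---|---|---|---|
| 0.5 | 0.8 | 4-7% | 29-34% | 80-88% |
| 0.5 | 1.2 | 13-21% | 61-73% | 69-80% |
| 0.5 | 1.6 | 26-42% | 80-93% | 53-68% |
| 0.5 | 2.0 | 40-69% | 88-99% | 30-54% |
| 0.8 | 1.2 | 19-38% | 79-91% | 57-76% |
| 0.8 | 2.0 | 42-79% | 92-100% | 20-54% |

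At 1.0 SD and correlation 0.5, separate simulation runs together give roughly 6-16% against about 46-56%.

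**6. Level with no change.** Stuart-Maxwell at nominal 5%: about 0.2-1.0% with rank-based df and 0-0.5% with 3 df when all four levels are used; about 2.6% with three levels; 1.3-5.3% with two. Exact ordered paired tests run at about 0.2-2.9%. Both are therefore mostly well below 5%. The gain in step 5 comes mainly from using the order of the levels.

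**The case against.** The strongest reply is that this is a pilot with descriptive aims and no single primary efficacy analysis, and that counts and percentages by group and time will be shown anyway. That is true and limits the harm. But the plan commits to this test for a primary endpoint and tells readers that 10 per group can show changes from baseline.

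It can also be said that the simulated sizes rest on inputs the documents do not give. That stands. For example, a mid-heavy score with correlation 0.8 gives Stuart-Maxwell about 53% power at 1.3 SD. The bound in step 2 and the tables in steps 3 and 4 do not depend on those inputs.

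Some stronger readings are tempting but unsupported:

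- *The test fails to keep the plan's 5% level.* A level below 5% does not breach a 5% limit; the cost is power. Moreover, the plan states alpha = 0.05 only for the two-sample t-test.
- *The test is too liberal in sparse tables.* The 4-of-10 table can mislead, but the highest level found with only two levels in use was 5.3%. The lesson is dependence on software, not general inflation.
- *The test always misses most real changes.* This fails for large shifts: at 2.0 SD the share missed is 20-54%.
- *Local immune activation has no other measure.* Tumor and nodal miR levels are also a primary endpoint (11.1, 3a), and section 8.3.4 describes a 0-300 infiltrate score.

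**Conclusion.** The point holds as a matter of test choice. The named test cannot make the between-group comparison that its sentence asks for. Within a group of 10, with all four levels in play, it cannot reach p < 0.05 unless at least 8 patients change level. For moderate shifts it would miss most of the changes that an exact ordered paired test would find. The exact results need only n = 10, the four-level score and a two-sided 5% threshold, which is an inference for this endpoint. The power figures also rest on the assumed level distributions and correlations. The relative loss shrinks as the shift grows, and generally with higher correlation or fewer levels in use. It is worth correcting before the tissue data are analysed, but it does not undermine the study.

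**What to change.** In section 11.2.2 item 3, replace the Stuart-Maxwell sentence with two tests on each patient's change in score (post minus pre, from −3 to +3):

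- **Within each HPV group:** an exact Wilcoxon signed-rank test, dropping zero changes and using the exact permutation distribution for ties. The rule for zeros must be written down: for 7 risers of 10, dropping zeros gives p = 0.016, whereas one package's alternative treatment of zeros returned 0.027.
- **Between HPV+ and HPV-:** an exact Wilcoxon rank-sum (permutation) test on the change scores.

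Report the numbers up, unchanged and down, and the median change, for each group. State the two-sided level that applies.

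The cost is a short rewrite of one item, with no new data or patients. The downside is small: both tests treat one-level steps as comparable and target a shift, so they would miss a pure spread of scores towards both extremes. The exact tests will also run below 5% at this sample size, so the counts should carry most of the interpretation.
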